5.5.2. Monitoring of Adverse Events with "diaries"

As the visit plan has considerable longer time intervals after the second half of the implantation, participants will be given a diary (such as a notebook) where they can briefly describe an

Silimed Indústria de Implantes Ltda

[name]

[contact] **[contact]

www.silimed.com.br • [contact] • facebook: silimed international/brasil

event, with the dates and arrangements that were made for each event. Suppose there is an event in which the participant visits another health professional, or does not seek any health professional because he/she considers that the AE does not need medical attention, the event may be registered by the participant and later verified by the investigator (or his/her delegate) with greater reliability.

The diary will have a purpose of physical memory of the event for the participant. The investigator (or any member of the team delegated by him/her) shall properly investigate the AEs recorded in the diary, together with reports, records or medical prescriptions related to that event, and record them properly on the appropriate form and on the database within the stipulated timeframes from perception of the AE.

The requested data of the diary are in an easy and accessible language for better understanding and completion of the participants. The investigator must guide the participant that it should be filled out, regardless of whether or not there was any adverse event (negative notification). If the participants have any AE (sign, symptom or medical event), even if there is no potential relation to the surgery or implant, it should be recorded in the diary. In each visit, a new diary will be given to the participants and the participants will be guided as to the correct way to fill out. The completed diary must be delivered to the Study doctor on the subsequent visit. The journals should be reviewed to confirm that all fields are complete and filled out correctly. The recorded data needs to be legible and with clear and concise information. The journals will be archived at participating centers and may be reviewed later by monitors.

If there is any AE in the diary, it should also be recorded in the respective medical record and additional information collected pertinent to its classification and resolution. Following the rationale of events ascertained in medical evaluations, events from the diary will also follow event nomenclature coding according to the MedDRA dictionary (<https://www.meddra.org/how-to-use/support-documentation/portuguese>). Participants should be oriented to immediately communicate to the study coordinators and / or investigators any and all SAE, as such events need to be reported to the Research Ethics Committee and ANVISA.

5.6. Secondary outcomes

Silimed Indústria de Implantes Ltda

[name]

[contact] **[contact]

www.silimed.com.br • [contact] • facebook: silimed international/brasil

5.6.1. Rosenberg self-esteem scale

To evaluate the overall self-esteem of the sample of this study, we will use the "Rosenberg Self-Esteem Scale" (RSES), translated and adapted to Portuguese.[34] This scale was initially developed by Rosenberg (1965) and results from a modification of Gutman's original scale (1953), in an attempt to achieve a one-dimensional measure of global self-esteem. This scale consists of ten items, of which five are positive and five are negative, however they are not presented consecutively to reduce the risk of targeted response and, in order not to induce the individual during filling. For each statement there are four possible answers: 1 - completely agree; 2 - agree; 3 - disagree; 4 - strongly disagree. For items 1, 3, 4, 7 and 10 (self-confidence) the score is as follows: completely agree = 0, agree = 1, disagree = 2 and strongly disagree = 3. Regarding items 2, 5, 8, and 9 (for self-depreciation) the score is as follows: completely agree = 3, agree = 2, disagree = 1 and completely disagree = 0. To obtain the total value for the global self-esteem, obtained in each of the items. The amplitude of the total scale value varies between 0 and 30 points. That way, the closer to 0 the better the self-esteem, and the closer to 30 the worse the self-esteem. Alternatively, for higher scores to represent better self-esteem and lower values represent lower self-esteem, it is enough to multiply the sum of the individual scores by -1 and add up to 30. Reversing the scale, higher the final result obtained, higher the self-esteem of each individual and vice versa. The Global Self-esteem Scale with values closer to 30 reflects an individual who feels good, that is, one feels equal to others, not necessarily superior to others, reflecting a global assessment of the individual about himself. Still, this scale adapts to the notion of multidimensionality of self-esteem and to the hierarchical structure defended today.

The Rosenberg scale correlates with the SRQ-20 (Self Reporting Questionnaire) instrument for assessing depression and with some dimensions of the SF-36 for estimating quality of life [34]. Despite this, there is evidence that there is no benefit in the self-esteem of incentive programs or interventions in adolescents in school programs. The use of self-esteem as an indicator of indiscriminate intervention can promote narcissism with its undesired consequences. [35]

1. De uma forma geral (apesar de tudo), estou satisfeito(a) comigo mesmo(a).
2. Às vezes, eu acho que eu não sirvo para nada (desqualificado(a) ou inferior em relação aos outros).
3. Eu sinto que eu tenho um tanto (um número) de boas qualidades.
4. Eu sou capaz de fazer coisas tão bem quanto a maioria das outras pessoas (desde que me ensinadas).
5. Não sinto satisfação nas coisas que realizei. Eu sinto que não tenho muito do que me orgulhar.
6. Às vezes, eu realmente me sinto inútil (incapaz de fazer as coisas).
7. Eu sinto que sou uma pessoa de valor, pelo menos num plano igual (num mesmo nível) às outras pessoas.
8. Não me dou o devido valor. Gostaria de ter mais respeito por mim mesmo(a).
9. Quase sempre eu estou inclinado(a) a achar que sou um(a) fracassado(a).
10. Eu tenho uma atitude positiva (pensamentos, atos e sentimentos positivos) em relação a mim mesmo(a).

Opções de Respostas:

- | | |
|------------------------|------------------------|
| a) Concordo plenamente | b) Concordo |
| c) Discordo | d) Discordo plenamente |

Afirmativas 1, 3, 4, 7, 10

- | | |
|---|------------------------|
| 0 | a) Concordo plenamente |
| 1 | b) Concordo |
| 2 | c) Discordo |
| 3 | d) Discordo plenamente |

Afirmativas 2, 5, 6, 8, 9

- | | |
|---|------------------------|
| 3 | a) Concordo plenamente |
| 2 | b) Concordo |
| 1 | c) Discordo |
| 0 | d) Discordo plenamente |

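### The written Rosenberg scoring rule in 5.6.1 omits item 6, so a score built from it runs 0 to 27, not the stated 0 to 30; the printed key in the same section includes the item.

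*Combined protocol and SAP*

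**What the plan says.** The Executive Summary lists the Rosenberg self-esteem scale among the secondary outcomes. Section 5.6.1 gives its scoring twice.

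- **English prose.** "This scale consists of ten items, of which five are positive and five are negative". Positive items: "For items 1, 3, 4, 7 and 10 (self-confidence) the score is as follows", from 0 (full agreement) to 3 (strong disagreement). Negative items: "Regarding items 2, 5, 8, and 9 (for self-depreciation) the score is as follows", from 3 down to 0. Range: "The amplitude of the total scale value varies between 0 and 30 points".
- **Portuguese questionnaire and key.** Item 6 is printed as "6. Às vezes, eu realmente me sinto inútil (incapaz de fazer as coisas", a negatively worded statement about sometimes feeling useless. The key groups the negative items as "Afirmativas 2, 5, 6, 8, 9" and scores them 3, 2, 1, 0.

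On direction, the prose first describes the raw sum: "the closer to 0 the better the self-esteem, and the closer to 30 the worse the self-esteem". It then offers, as an alternative, a reversed score equal to 30 minus the sum. Right after that it says: "The Global Self-esteem Scale with values closer to 30 reflects an individual who feels good".

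Section 5.9 plans trajectories over time, by implant group, for secondary outcomes measured on continuous scales. It does not say which direction of the Rosenberg score will be used.

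**The concern.** Section 5.6.1 is the operative definition of a named secondary outcome. It contains two item lists that give different totals for the same answers. The prose is in English and the key in Portuguese, so two people working from one section could compute two different scores. The prose sentence meant to define the total is itself incomplete, so it does not repair the omission.

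Section 6.4.2 lists Form 08, which carries the scale, at every scheduled on-site visit over ten years, and section 5.11 repeats the final analyses each year. A wrong item list would therefore recur in every report. If the list changed between reports, the curve could shift with no change in the women's answers.

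A smaller matter sits beside this one. Two opposite scorings are described and neither is named for analysis, so the meaning of a rising curve is not fixed in advance.

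**Working it through.** **Inputs, all from 5.6.1.** Each item scores 0 to 3. Positive items: 1, 3, 4, 7, 10 (five, the same in prose and key). Negative items: 2, 5, 8, 9 in the prose (four) and 2, 5, 6, 8, 9 in the key (five). Reversal: 30 minus the sum.

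**Formulas.** Raw maximum = 3 × number of scored items; raw minimum = 0. Reversed range = (30 − raw maximum) to (30 − raw minimum).

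**Reproducing the stated range from the key.** Items scored: 5 + 5 = 10. Raw maximum: 3 × 10 = 30. The raw range is 0 to 30, which matches the plan. Reversed: 30 − 30 = 0 to 30 − 0 = 30.

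**Same steps from the prose list.** Items scored: 5 + 4 = 9, with item 6 missing. Raw maximum: 3 × 9 = 27. The raw range is 0 to 27. Reversed: 30 − 27 = 3 to 30 − 0 = 30.

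| Source | Items | Raw range | Reversed range |
|---|---|---|---|
| Printed key | 10 | 0 to 30 | 0 to 30 |
| Prose list | 9 | 0 to 27 | 3 to 30 |

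**Size for one woman.** Let *x* be her item 6 score, 0 to 3. The prose raw total is too low by *x*, and the prose reversed total is too high by *x*. The largest error is 3 points, and 3/30 = 10% of the range. With the best answer to item 6, *x* = 0 and there is no error. With the worst answers throughout, the reversed score is 3 instead of 0.

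**Direction.** For two raw sums S₁ and S₀, the reversed difference is (30 − S₁) − (30 − S₀) = −(S₁ − S₀). Only the sign changes; the size of the difference, its standard error and its interval width stay the same.

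**The case against.** The strongest reply is that the plan does score item 6. The key in the same section includes it, and the prose itself gives five negative items and a 0 to 30 total. Three statements agree on ten items and one list drops a number, so this is most likely a drafting or translation slip. The stated range is correct, and the Form 08 calculation is not in the documents, so nothing shows that it follows the prose. All of this stands, and it limits the point to an error in the prose list. It does not remove that error: the list is given as a scoring rule and contradicts the rest of its own section.

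A reader might infer three stronger things that the documents do not support.

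- *That the trial leaves item 6 unscored, or that its data will run 0 to 27.* The key scores the item; 0 to 27 arises only if the prose list is followed.
- *That the two directions contradict each other.* The second is introduced as an alternative, its conversion is valid, and the remark about values near 30 follows the reversal and reads naturally as describing it. What is missing is a choice between the two.
- *That the reversed score is required so as to match the BEQ.* The BEQ satisfaction and comfort items do run upward to 5 as best (5.6.2). The satisfaction scale in 5.6.3 runs the other way, with 1 as best, and the patient's satisfaction rating shares Form 08 with the Rosenberg scale. The choice is the sponsor's.

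**Conclusion.** The point holds for the prose scoring rule. As written it covers nine of ten items and cannot produce the range stated in the same paragraph. The consequence is conditional: a score programmed from the prose would be wrong by 0 to 3 points per woman per visit, while a score programmed from the key would be right. The effect on a group mean, or on the difference between the implant groups, depends on the item 6 answers, which the documents cannot supply.

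The unnamed direction is missing detail. The two versions are mirror images with the same precision, and 5.9 sets no directional hypothesis or margin for this scale. It still needs stating, so that the sign of a reported change can be read without guessing.

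This rests on two assumptions: that the key shows the intended scoring, as the five-negative count and the 0 to 30 range indicate, and that each item is scored 0 to 3 as both sources say. The point is confined to one secondary outcome.

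**What to change.** In the prose of 5.6.1, change the list of negative items to 2, 5, 6, 8 and 9 so that it matches the key, and complete the unfinished sentence that defines the total as the sum of the ten item scores. Check that the Form 08 calculation uses all ten items.

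As the accompanying clarification, state in 5.6.1 and 5.9 which score is analysed and reported: the raw sum (0 = best) or 30 minus the sum (30 = best). Keep that choice in every annual report and label the axis accordingly.

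The cost is a few lines of text and one check of the electronic form. If Form 08 proves to have used nine items and the item-level answers are stored, the scores can be recomputed without new data collection.

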5.6.2. Breast Evaluation Questionnaire (BEQ-Brazil)

The Breast Evaluation Questionnaire (BEQ 55) was developed in 2006 in the English language and includes 55 questions related to satisfaction and comfort with the overall appearance of the breasts. In 2013, the BEQ was validated cross-culturally for use in the Portuguese language. [35]

BEQ 55 is a self-administered questionnaire of 55 questions developed to evaluate breast satisfaction and changes in quality of life in patients undergoing breast surgery. The answers are given in scales with five ranks, with 1 corresponding to very dissatisfied or very uncomfortable and 5, to very satisfied or very comfortable. It consists of three parts. The first part questions the satisfaction with size, shape and firmness of the breasts in different situations: sexual, social or professional activities. The second part checks for the degree of comfort with the overall appearance or appearance of the breasts when fully clothed, in bathing suits or naked, being alone, with intimate partner, with men in general, women in their relationship, not so intimate or professional women of health. The third part contains two questions, the first requesting to give the level of satisfaction with the appearance of the breasts to themselves, their partner, parents, siblings and friends. The final question asks to rate how important the size of your breasts is to yourself and the people in your relationship.

QUESTIONARIO DE AVALIAÇÃO DAS MAMAS (BEQ 55)

À paciente: Anote o número mais adequado para sua resposta. Use uma única alternativa por resposta. Favor responder todas as perguntas. Não deixe nenhum item em branco.

1. Qual é o seu grau de satisfação com cada um dos seguintes itens?
Por favor, avalie as questões preenchendo o número conforme a escala abaixo:

- 1 = Muito Insatisfeita
2 = Um Pouco Insatisfeita
3 = Nem Satisfeta Nem Insatisfeta
4 = Razoavelmente Satisfeta
5 = Muito Satisfeta

Com o tamanho das suas mamas?

Durante atividades íntimas ou sexuais _____
Durante atividades sociais ou de lazer _____
Durante atividades profissionais ou de trabalho _____

Com o formato das suas mamas?

Durante atividades íntimas ou sexuais _____
Durante atividades sociais ou de lazer _____
Durante atividades profissionais ou de trabalho _____

Com a firmeza das suas mamas?

Durante atividades íntimas ou sexuais _____
Durante atividades sociais ou de lazer _____
Durante atividades profissionais ou de trabalho _____

2. Como você se sente quanto ao conforto ou desconforto em cada um dos seguintes itens, estando sozinha, com seu namorado ou parceiro íntimo, com outras mulheres do seu relacionamento (familia ou amigas), com homens em geral, com mulheres menos íntimas (academia ou vestiário) ou com profissionais da saúde (médicos ou enfermeiras)?

Por favor, avalie as questões preenchendo o número conforme a escala abaixo:

- 1 = Muito Desconfortável
2 = Um Pouco Desconfortável
3 = Nem Confortável Nem Desconfortável
4 = Razoavelmente Confortável
5 = Muito Confortável

Quanto à sua aparência geral (corpo todo) quando está totalmente vestida?

Sozinha _____
Com seu marido ou parceiro _____
Com homens em geral _____
Com mulheres do seu relacionamento _____
Com mulheres menos íntimas _____
Com profissionais da saúde _____

Quanto à sua aparência geral (corpo todo) de maiô ou biquíni?

Sozinha _____
Com seu marido ou parceiro _____
Com homens em geral _____
Com mulheres do seu relacionamento _____
Com mulheres menos íntimas _____
Com profissionais da saúde _____

Quanto à sua aparência geral (corpo todo) despida (sem roupas)?

Sozinha _____
Com seu marido ou parceiro _____

Com homens em geral _____
Com mulheres do seu relacionamento _____
Com mulheres menos íntimas _____
Com profissionais da saúde _____

Quanto à aparência de suas mamas quando totalmente vestida?

Sozinha _____
Com seu marido ou parceiro _____
Com homens em geral _____
Com mulheres do seu relacionamento _____
Com mulheres menos íntimas _____
Com profissionais da saúde _____

Quanto à aparência de suas mamas quando está de maiô ou biquíni?

Sozinha _____
Com seu marido ou parceiro _____
Com homens em geral _____
Com mulheres do seu relacionamento _____
Com mulheres menos íntimas _____
Com profissionais da saúde _____

Quanto à aparência de suas mamas quando está despida (sem roupas)?

Sozinha _____
Com seu marido ou parceiro _____
Com homens em geral _____
Com mulheres do seu relacionamento _____
Com mulheres menos íntimas _____
Com profissionais da saúde _____

3. Você e as pessoas ligadas a você estão satisfeitas com a aparência (visual) das suas mamas?

Por favor, avalie as questões preenchendo o número conforme a escala abaixo:

- 1 = Muito Insatisfeito(a)
2 = Um Pouco Insatisfeito(a)
3 = Nem Satisfeto(a) Nem Insatisfeto(a)
4 = Razoavelmente Satisfeto(a)
5 = Muito Satisfeto(a)

Para você mesma _____

Para seu marido ou parceiro sexual _____
Mãe ou pai (aquele que você considera mais a opinião) _____
Irmã(s, o, os) (aquele que você considera mais a opinião) _____
Amigo(a, os, as) (aquele que você considera mais a opinião) _____

4. Você e as pessoas ligadas a você dão importância ao tamanho das suas mamas (reparam)?

Por favor, avalie as questões preenchendo o número conforme a escala abaixo:

- 1 = Totalmente Sem Importância
2 = Pouco Importante
3 = Nem Importante Nem Sem Importância
4 = Razoavelmente Importante
5 = Muito Importante

Para você mesma _____

Para seu marido ou parceiro sexual _____
Mãe ou pai (aquele que você considera mais a opinião) _____
Irmã(s, o, os) (aquele que você considera mais a opinião) _____
Amigo(a, os, as) (aquele que você considera mais a opinião) _____

5.6.3. Satisfaction evaluation

Satisfaction regarding the aesthetic result of the surgery is evaluated by both the participant and the evaluating physician in all the on-site visits planned in the follow-up. To measure satisfaction, a Likert scale will be used where the following satisfaction options can be selected: 1 = definitely satisfied, 2 = satisfied, 3 = slightly satisfied, 4 = slightly dissatisfied and 5 = definitely unsatisfied.

Silimed Indústria de Implantes Ltda

[name]

[contact] [contact]

www.silimed.com.br • [contact] • facebook: silimed international/brasil

5.7. Allocation for treatment

As this study is being characterized as phase IV, and participants are being included after implantation, the allocation of the participant to a type of implant will be performed by the participant's attending physician according to his/her technical judgment considering the reasons for the implantation and clinical characteristics involved in each case, without sponsor interference. There will be no restriction on the shape or size of the implant.

5.8. Masking / Blinding

In the study in question, there will be no masking / blinding. This is justified, since the main reason for masking is to make the verification of the outcome less biased, especially for the outcomes that are operator dependent and for the outcomes that have intermediate / doubtful results. There are at least 3 types of masking, (a) masking in which the participant does not know what intervention is received, (b) masking in which the professional in charge of the outcome does not know what intervention the participant receives, and (c) masking who does the data analysis does not know which group the participants were allocated to.

In this study there are two important elements that difficult the masking in such way that it was considered impracticable or irrelevant this procedure. The first is that the participants will be recruited after implantation, so that they are already aware of which type of implant to include in the study. The second is that benefit-related outcomes as well as outcomes of expected events will be reported by the participant to the practitioner who handles the outcome in the event "diaries" or face-to-face assessments.

5.9. Statistical analysis plan

The statistical analysis will be divided into two parts, one descriptive and one analytical. The descriptive part will consist of showing counts and fractions of categorical variables and central tendencies (mean + standard deviation or median + interquartile range) of continuous variables recorded at the beginning of the follow-up by the groups of major interest. The groups of major interest are formed by the indication of implantation and the type of implant (primary augmentation
Silimed Indústria de Implantes Ltda

[name]

[contact] **[contact]

www.silimed.com.br • [contact] • facebook: silimed international/brasil

with textured surface implant, primary augmentation with polyurethane foam-coated surface implant). In addition, for the purpose of exploring heterogeneity this approach will also be done by participant center.

The initial statistical analysis for the analytical part is to estimate the risks (cumulative probabilities up to a follow-up time) and their respective confidence intervals of unwanted (expected and not expected) events in general and interest-specific ones (e.g. capsular contracture in the textured implants group, in the polyurethane implants group, mild events, serious events, events with probable causality, etc.), as well as events of different intensities (mild, moderate, severe, etc.). The accumulated risks up to the first events in the period of interest will be estimated through the Kaplan-Meier estimator. This analysis should consider the patient as an observation unit, and then the same approach will consider the breast as an observation unit.

The incidence density estimate (incidence rate = (number of events / person-year) x 100) over a period of time, accumulated from the beginning of the follow-up and decomposed by the year of follow-up, will have the same rationale as the risk estimate, in the same patient groups and types of events, and will disregard the difference between incidence and recurrence of events as well as the period in which the participants were not at risk. This approach will allow estimating the incidence over a cumulative period (e.g. from the beginning of the follow-up) as well as decomposing the incidence into different periods (e.g. incidence in the second or third year of follow-up). In the same way as the previous approach, this analysis will consider a volunteer as an observation unit, then the same approach will consider a breast as the unit of observation.

The additional strategy for estimating the "hazard" for each of the most significant adverse events is to use a multiple model that allows the adjustment of each group's "hazard" for each event of major interest in the follow-up period by elements that could modify the prognosis of the volunteers or confuse the "hazard" estimate. These elements are described above in the section on "descriptive characteristics that could interfere with the prognosis".

Secondary outcomes, related to the desired effect of implants, that will be measured as continuous scales will be analyzed as trajectories over time. To this purpose, the individual crude trajectories of each participant will be verified, then the means / medians and their respective confidence intervals will be estimated at each follow-up time, and finally the marginal trajectories adjusted for correlation of each group (formed by each type of implant - textured and polyurethane)

Silimed Indústria de Implantes Ltda

[name]

[contact] **[contact]

www.silimed.com.br • [contact] • facebook: silimed international/brasil

will be estimated, always having the follow - up time as a predictor.

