The table below contains the limit reference values for the comparison of cumulative risks to be estimated by the Kaplan-Meier method. Risks will be compared as proportions and the alarm will be given if there is a significance difference at 1%. The reference limits were refereed considering data from the literature with implants of the brand SILIMED and reports of registration of similar products. In the literature, the risk of capsular contracture with SILIMED implants varies in the different studies, but is usually low (1% in 10 years [39], 0.40% in 15 years [40], 8.8% in 5 years [41], 11.2% at 8 years [42], 12% at 9 years [38]). The risk of surgery for implant removal is also low (1.2% for 15 years [40], 16% for 5 years [41], 12% for 8 years [42], 13.9% for 9 years [38]). With these values, an initial core trend value was estimated, i.e. from the first year, a risk of 5% was added. For the following years, i.e. from the second to the tenth year of follow-up, a threshold value was added which indicates the cumulative increase in risk for each event. The initial limits of comparison considered were 6.30%, 6.85% and 5.65% for capsular contracture, removal with replacement and removal without replacement, respectively. The progressive increase for each of these three events are: 1.00%, 1.25% and 0.175% per year.

Table - Reference limits of the risk of event to alarm in the intermediate evaluations.

Year	Capsular contracture	Removal with replacement	Removal without replacement
1	6,30%	6,85%	5,65%
2	7,30%	8,10%	5,83%
3	8,30%	9,35%	6,00%
4	9,30%	10,60%	6,18%
5	10,30%	11,85%	6,35%
6	11,30%	13,10%	6,53%
7	12,30%	14,35%	6,71%

Silimed Indústria de Implantes Ltda

[name]

[contact] [contact]

www.silimed.com.br • [contact] • facebook: silimed international/brasil

8	13,30%	15,60%	6,89%
9	14,30%	16,85%	7,07%
10	15,30%	18,10%	7,25%

5.12. Quality criteria for data management and periodic reports.

Data quality should be verified in a stratified form, and the following indicators are considered as minimum elements, including quality indicators.

1. Total number of participants since the beginning of the recruitment, and number of participants in the previous 30 days.
2. Number (fractions) of visits made within the windows provided from the beginning and in the last 30 days.
3. Number (fractions) of fields with missing or inconsistent data.

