6.5. Discontinuation

6.5.1. Discontinuation of participants

Participation of the volunteer in the study may be discontinued at any time, at the discretion of the investigator/sponsor and by decision of the participant. If study participation is discontinued, all outcome data should be collected in accordance with the study procedures schedule. The sponsor will be notified of all cases of withdrawal or interruption of participant.

The reasons why the investigator or sponsor may withdraw a study participant include the following:

- AE, which according to the Principal Investigator's judgment, renders participation in the study unsafe for the participant.
- Severe protocol violation.
- Study closure by sponsor.
- Withdrawal of consent (option of participant).
- Removal or replacement of breast implants even if requested by the participant.
- Other aesthetic interventions in the breasts.
- Participation in another clinical investigation with experimental intervention.
- Events that compromise cognition or ability to understand in a persistently or permanently way, (e.g. Alzheimer's disease, stroke, or traumatic brain injury), in a way that impedes the provision of reliable data regarding follow-up.
- Loss of follow-up of the participant, defined as non-attendance in face-to-face evaluations for a period equal to or greater than two years, or two windows of face-to-face visits after the first year of follow-up.

Any participant (or his/her legal representative) may withdraw consent to participate in the study at any time, without prejudice to the participant. The investigator will need to withdraw any participant requesting withdrawal from the study. If a participant withdraws consent, all appropriate outcome and safety assessments at the time of withdrawal of the participant should be obtained if possible. The evaluations listed in the Study Procedures Schedule for the early termination visit should be performed, as applicable.

Every effort should be made to keep volunteers as participants in the study. If a participant

Silimed Indústria de Implantes Ltda

[name]

[contact] [contact]

www.silimed.com.br • [contact] • facebook: silimed international/brasil

fails to return for scheduled visits, a documented effort must be made to determine the reason. If a participant withdraws before completing the study, the reason for withdrawal should be documented in the CRF.

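### Kaplan-Meier risks in 5.9 have no rule for explantation as a competing event; if explants are censored, contracture, rupture and each removal type are modestly overstated

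*Combined protocol and SAP*

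**What the plan says.** Section 5.9 gives the first analytical aim as to "estimate the risks (cumulative probabilities up to a follow-up time") with confidence intervals, for adverse events overall and for specific ones such as contracture by implant type. The estimator follows: "The accumulated risks up to the first events in the period of interest will be estimated through the Kaplan-Meier estimator". On the unit it says: "This analysis should consider the patient as an observation unit, and then the same approach will consider the breast as an observation unit".

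Section 5.11 uses the same quantities for the yearly alarms on contracture, removal with replacement and removal without replacement. Its table serves the "comparison of cumulative risks to be estimated by the Kaplan-Meier method".

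Section 6.5.1 introduces its list of withdrawal reasons with "The reasons why the investigator or sponsor may withdraw a study participant include the following", and one entry is "Removal or replacement of breast implants even if requested by the participant". The same section also says: "If study participation is discontinued, all outcome data should be collected in accordance with the study procedures schedule".

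No section mentions competing risks or a cumulative incidence function, and none gives a censoring rule for explantation. The nearest statement is in 5.9, which disregards recurrence "as well as the period in which the participants were not at risk", but that applies only to the incidence rate per person-year.

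**The concern.** An implant that has been taken out can no longer rupture or develop contracture. For one implant, first removal with replacement and first removal without replacement are alternatives. Section 5.5 adds that a removal done only at the patient's request is not an adverse event, so it never appears as an event in the adverse-event curves although it ends that implant's risk.

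Kaplan-Meier with such breasts censored assumes that they would have gone on to have the event at the same rate as breasts still carrying the implant. It then describes risk in a population in which nobody is explanted. That can be a legitimate device question, but it is not the cumulative probability that 5.9 names. What is at stake is a systematic upward shift in some long-term headline risks, and separate removal curves that add up to more than total removal.

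**Working it through.** The plan gives no figure of its own on this point, so there is none to reproduce. The check uses the plan's rates.

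**Inputs**
- 9-year augmentation risks, 5.10: contracture 12.0%, removal 13.9%, rupture 4.3%. The documents do not say how these were estimated; they are taken here as Kaplan-Meier risks.
- Minimum size per group, 5.10: 246 women, used as given.
- Year-10 alarm limits, 5.11: contracture 15.30%, removal with replacement 18.10%, removal without replacement 7.25%.
- Death is left out because the documents give no rate.

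**Formula.** Let p1 be the Kaplan-Meier risk of the event, p2 that of explantation, and λ = −ln(1 − p). With independent constant hazards, the cumulative incidence is

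CIF = λ1/(λ1 + λ2) × [1 − (1 − p1)(1 − p2)].

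With independent hazards of any shape, the excess p1 − CIF lies between 0 (all explants late) and p1 × p2 (all explants first).

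**9 years, all removals competing**
- Contracture: λ1 = −ln 0.88 = 0.1278; λ2 = −ln 0.861 = 0.1497; 1 − 0.88 × 0.861 = 0.2423. CIF = 0.1278/0.2775 × 0.2423 = 11.16%. Excess 0.84 points; upper bound 0.12 × 0.139 = 1.67 points.
- Rupture: λ1 = −ln 0.957 = 0.0440; 1 − 0.957 × 0.861 = 0.1760. CIF = 0.0440/0.1936 × 0.1760 = 4.00%. Excess 0.30 points; upper bound 0.60.

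**9 years, half the removal hazard competing.** Section 2.3 calls intense contracture the most frequent indication for removal. Those removals follow the event and do not compete with it. With λ2 = 0.0748, CIF = 0.1278/0.2027 × 0.1834 = 11.57%, an excess of 0.43 points.

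**Checks on the assumptions.** A simulation of 200,000 subjects with 40% loss to follow-up gave 12.0% by Kaplan-Meier and 11.2% by Aalen-Johansen at 9 years. With a shared gamma frailty of variance 1 (assumed), so that women prone to contracture are also prone to removal, the figures were 10.6% and 10.0%. The direction is the same.

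**Against the precision.** The 95% half-width at 12.0% is 1.96 × √(0.12 × 0.88/246) = 4.1 points; for rupture at 4.3% it is 2.5 points. If the two breasts of each woman were fully independent, giving 492 units, the contracture figure would still be 4.06/√2 = 2.9 points.

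**Early reports.** Using 3-year registration figures in 2.3, contracture of 2.1% with removals of 0.5% and 5.0% has an excess of 0.06 points. Contracture of 8.1% with removals of 2.3% and 2.8% has an excess of 0.20 points.

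**At the year-10 alarm limits**

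| Event | 1 − KM | Competing risk | CIF | Excess (points) |
|---|---|---|---|---|
| Contracture | 15.3% | 1 − 0.819 × 0.9275 = 24.0% | 13.4% | 1.9 |
| Removal without replacement | 7.25% | 18.1% | 6.6% | 0.7 |
| Removal with replacement | 18.1% | 7.25% | 17.5% | 0.6 |

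The two removal incidences, 6.58% and 17.46%, add to the combined 24.04%. The two Kaplan-Meier figures add to 25.35%.

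**The case against.** **The censoring is not in the documents.** A reader might infer that the plan treats explantation as ordinary censoring. It does not say so. Withdrawal after removal is permitted, not required; 6.5.1 asks for outcome data after discontinuation; and 5.5 plans recurrence risk by treatment of the first event, which presupposes some follow-up after treatment. This stands: the documented defect is a missing rule, and the bias is conditional on how that gap is filled.

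**The scope is limited.** It is tempting to say that every event-specific risk is inflated. Any reoperation and any removal count explantation as an event and are unaffected. Hematoma, delayed healing and similar complications occur mostly early, before many explants. Pain or rash can still occur afterwards. It is equally tempting to say that the two removal types exclude each other. That fails for the patient, who may have one side replaced and the other not, and who stays at risk on the side not explanted. In the 7-year augmentation column of 2.3 the two types sum to 12.7% against 12.6% combined, which rounding could explain.

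**A larger size is not supported.** Someone might take the 22.2% reoperation risk in 5.10 as the competing event. Section 5.5 distinguishes surgical treatment with and without explantation. A woman reoperated on with her implant in place can still develop contracture, so that scenario does not belong here.

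**The comparison between surfaces is barely touched.** With assumed removal of 13.9% in one group and 7% in the other, the contracture excesses are 0.84 and 0.42 points, a difference of 0.4. Section 5.10 assumes equal risks, and 5.9 also plans an adjusted hazard model.

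**Changing the alarm could do harm.** The limits in 5.11 come from literature and registration reports whose estimators are not stated. Replacing Kaplan-Meier there would lower the monitored contracture figure (15.3% to 13.4% at the year-10 limits) against unchanged limits and make the alarm less sensitive. This stands. Any Kaplan-Meier excess errs towards extra alarms.

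**Conclusion.** The point holds in limited form and is minor. Section 5.9 names a cumulative probability, chooses an estimator that matches it only if nothing removes a breast from risk, and does not say what happens at explantation. If explants are censored, the risks of contracture, rupture and each removal type are overstated. At the plan's 9-year rates the excess is about 0.4 to 0.8 points for contracture and up to about 0.3 for rupture, well inside the planned intervals. It does not shrink as the sample grows, and it increases with follow-up and removal.

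These sizes rest on independent constant hazards, on reading the cited 9-year risks as Kaplan-Meier figures, and on explants being censored. The documents do not support a claim that all primary risks are biased, that the comparison of surfaces is materially distorted, or that the 5.11 alarm should change estimator.

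**What to change.** In 5.9:
- State how an explanted breast is handled in the first-event analyses, including whether a breast with a replacement implant is still followed or leaves the risk set of the original implant. Reconcile this with the withdrawal and data-collection statements in 6.5.1.
- With the breast as unit, report Aalen-Johansen cumulative incidence for contracture, rupture and each removal type. For contracture and rupture, the competing events are explantation before the event and death. For each removal type, they are the other type and death. Intervals should allow for two breasts per woman.
- Keep Kaplan-Meier beside it for comparison with the literature.

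In 5.11, keep the Kaplan-Meier comparison with the existing limits and show the Aalen-Johansen estimate as supporting information only. Do not substitute it unless the limits are re-derived on the same scale.

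The cost is a few sentences and a small amount of programming. It uses explantation and adverse-event data that 5.5 and 5.5.1 already collect. The downside is a second set of estimates to report and explain.
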